This study is an open-label, randomized controlled trial. Patients will be randomized into two groups of 15, "Routine Care" group, which will serve as the control group, and "Octreotide" group. The amount of bronchial secretions is routinely measured in all mechanically ventilated patients. Once the Primary Team identifies a patient as a candidate for the study, the study team will review their medical records and assess the patient based on the inclusion and exclusion criteria to determine if they are qualified to participate in the study (screening). If the patient is qualified, one of the study members will explain the research project to the patient or his/her authorized representative and also explain the informed consent process. This study does not compensate patients for participating in the study or for any potential injuries/illness arising out of their participation in this study. This aspect will be made clear to the patients (or their authorized representative) in addition to other risks and benefits of participation in this study. If the patient or his/her authorized representative agrees to participate in the study informed consent will be obtained. After informed consent, the patient will be administered

standard of care medications for the first 24 hours after the screening and a baseline volume of bronchial secretions during this 24 hour period will be recorded. Additionally, medications administered and procedures performed during this 24 hour period would also be recorded. Then, a security envelope containing group assignment will be opened by the ICU attending physician. Both groups will continue to receive treatments that have already been initiated to manage bronchial secretions. In addition, "Octreotide" group will receive parenteral octreotide, while "Routine Care" group will not receive any additional treatment for the study. All patients will continue to receive the care deemed necessary by the ICU attending physician and his/her team. These interventions will be continued for 72 hours or until extubation or withdrawal from the study, whichever occurs earlier. Subsequently, the standard of care management, as determined by the Primary Team, will be continued.

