Baseline volume of bronchial secretions suctioned over a 24-hour period will be recorded for all subjects, and interventions prescribed by the random treatment assignment will be initiated and continued for up to 72 hours. Simultaneously, the rate of secretions will be measured and recorded (by registered nurses taking care of the patients) during each 24-hour shift. Volume of normal saline used to flush endotracheal tube will be recorded and then subtracted from the total volume found in the suction container in the end of each shift. Effectiveness of the interventions studied in this trial will be determined by comparing the percent change in the secretions rate (relative to the baseline rate) between the “Octreotide” and “Routine group” subjects, which will be the primary outcome. The secondary outcome will be the percentage of patients who were extubated within 72 hours after initiating the interventions (“Octreotide” vs “Routine”).

Assessment of Safety:

The study will be performed in mechanically ventilated patients in an ICU, an environment where close monitoring of all patients in an absolute requirement. Similarly to the patients in the control arm, subjects in the treatment arm will be closely monitored for adverse reactions of octreotide. Close monitoring includes continuous and periodic monitoring of vital signs including Heart Rate, Blood Pressure and Respiratory Rate. Based on these data, as well as results of serum chemistry performed at least daily (which is part of the standard care in ICU), doses of beta-blockers, calcium channel blockers, insulin, and agents to control fluid and electrolyte balance will be adjusted, - similarly to situations when octreotide is used for other medical conditions.

Given the reported adverse reactions of octreotide, an electrocardiogram will reviewed for each subject, and patients with bradycardia and significant conduction defects will be excluded (see the exclusion criteria). During the study, vital signs will be monitored every hour, and cardiac activity will be continuously monitored by telemetry. To confirm timely assessment of safety,

the study team will ensure that the vital signs data are recorded every 4 hours in the data collection tool.

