If a patient develops bradycardia (HR < 60 bpm), octreotide administration will be stopped and the patient will be withdrawn from the study. Furthermore, if a subject experiences increase in systolic BP to 180 mmHg or above, octreotide administration will be stopped and the patient will be withdrawn from the study. However, if a subject experiences increase in systolic BP by at least 40mmHg over 2 hours, the infusion rate will be decreased to 12 mcg/hr; the BP will be reassessed every hour, and the infusion rate will be titrated up as tolerated to a maximum of 25mcg. Given octreotide's effect on serum glucose level, all subject's capillary blood glucose (CBG) will be monitored every 4 hours to monitor for hyperglycemia and hypoglycemia. The glucose levels every 4 hours will be recorded in the data collection form. Subjects who are hyperglycemic and require more than 20 units of intravenous insulin per hour will be withdrawn from the study, as will subjects who experience hypoglycemia (CBG < 60 mg/dL) despite being on 5% dextrose drip.

Statistical analysis:

Data will be analyzed with the assistance of a statistician at Danbury Hospital's Department of Research and Innovation. The differences between the two groups (Routine Care vs. Octreotide) in the percentage change of rate of secretion (defined as milliliters per 24 hours) for each of the 24-hour periods as compared to the baseline 24-hour period and proportion of patients extubated within 72 hours (defined as both time to extubation AND yes/no extubated within 72 hours) will be compared. The Fisher's exact test will be used to assess statistical significance (alpha set at $p < 0.05$). If the sample size allows and there are adequate cell frequencies, regression analyses will be used to assess the association between the use of Octreotide and the primary outcome variables.

Given that no previous research has been conducted to examine management of bronchorrhoea resistant to conventional interventions in mechanically ventilated patients, a power calculation to estimate the sample size cannot be performed reliably. We do recognize the small sample size to be included in our study and intend for this project to serve as a pilot study that would provide some evidence-based information to guide clinicians at our institution in such situations and provide background information for further studies on a much larger scale.

References:

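### The primary outcome, percent change in secretion rate, has no applicable test; the only suitable analysis (regression) is conditional and does not name the baseline that every patient has.

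*Combined protocol and SAP*

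**What the plan says.** - **Outcome.** Assessment of Efficacy bases effectiveness on "comparing the percent change in the secretions rate (relative to the baseline rate") between the two arms and calls this the primary outcome. Statistical analysis applies it "for each of the 24-hour periods as compared to the baseline 24-hour period", which is up to three periods over 72 hours.
- **Baseline.** Assessment of Efficacy states: "Baseline volume of bronchial secretions suctioned over a 24-hour period will be recorded for all subjects". Recorded saline flush is subtracted from the container volume.
- **Test.** Statistical analysis names one test: "The Fisher's exact test will be used to assess statistical significance". It gives no cut-off that would turn percent change into a yes/no outcome.
- **Regression.** "If the sample size allows and there are adequate cell frequencies, regression analyses will be used to assess the association" between octreotide use and the primary outcome variables. Baseline volume is not listed as a covariate.
- **Size.** Trial Design: "Patients will be randomized into two groups of 15". Statistical analysis says that power cannot be calculated reliably and describes the project as a pilot.

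**The concern.** Fisher's exact test compares proportions. It suits extubation by 72 hours, but percent change in ml per 24 hours is continuous. The plan as written therefore has no usable test for its primary outcome unless someone chooses a cut-off or invokes the regression clause. Both choices would be made after the data are seen.

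The regression clause does not close the gap. Cell frequencies have no meaning for a continuous outcome, and a regression on treatment alone would still ignore baseline as a covariate. Dividing by a single 24-hour suction volume carries the error in that volume into every patient's result and skews the ratio to the right.

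With 30 patients precision is scarce, and the data for a better analysis are already being collected. The plan wants the results to guide local clinicians and inform larger studies. Both uses need a precise estimate with an interval.

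**Working it through.** **1. Figure to reproduce.** There is none. The documents give no power, effect size, spread or baseline/follow-up correlation.

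**2. Inputs.** From the documents: 15 per arm (Trial Design); baseline in all subjects (Assessment of Efficacy); entry threshold above 200 ml/24 h (Inclusion criteria); alpha 0.05 (Statistical analysis). Assumed: two-sided test, log-normal volumes, median 300 ml, coefficient of variation (CV) 40-80%, correlation ρ 0.3-0.7, true reduction 40%, one post-baseline period, nobody missing, no zero net volumes.

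**3. Is sample size a barrier?** Intercept, arm and baseline are three parameters. Residual degrees of freedom are 30 − 3 = 27, against 28 for a two-sample t-test. The model can be fitted.

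**4. Closed form, linear case.** Var(change) = 2σ²(1 − ρ). Var(baseline-adjusted) = σ²(1 − ρ²). Their ratio, adjusted to change, is (1 + ρ)/2, which never exceeds 1.

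| ρ | (1 + ρ)/2 | Largest power loss at 15 per arm |
|---|---|---|
| 0.3 | 0.65 | 18 points |
| 0.5 | 0.75 | 12 points |
| 0.7 | 0.85 | 7 points |

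At ρ = 0.3 adjustment needs 0.65 × 30 = 19.5 patients to match change scores in 30. The largest loss is 25 points at ρ = 0.1 and 2 points at ρ = 0.9.

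**5. Simulation on the percent-change scale.** 5,000 trials per setting, 40% reduction. Power of a t-test on percent change v a linear model of log volume on arm and log baseline (log-ANCOVA):

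| CV, ρ | Baseline unrestricted | All baselines above 200 ml |
|---|---|---|
| 60%, 0.5 | 63% v 79% (16 points) | 68% v 79% (11) |
| 80%, 0.3 | 28% v 51% (23) | 36% v 50% (14) |
| 40%, 0.7 | 99% v 99.8% (about 1) | 99.6% v 99.8% (0.2) |

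Repeat runs moved these by about 1 to 2 points, and the 14-point gap came out at 15 in one of them. Type I error of log-ANCOVA was 4.5-5.8%.

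**6. Source of the gap.** At CV 60%, ρ 0.5 and baselines above 200 ml, one run gave 69% for percent change, 74% for a t-test on log change and 80% for log-ANCOVA. So 74 − 69 = 5 points come from the scale and 80 − 74 = 6 from baseline adjustment.

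**7. The named test.** At log-SD 0.5, ρ 0.3, a 40% reduction and baselines above 200 ml, Fisher's test on a dichotomised change has 34% power with a 30% cut-off and 28% with a 50% cut-off. The t-test on percent change has 65% and log-ANCOVA 80%.

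**8. Zero volumes.** Saline is subtracted, and the Background cites a case in which sputum stopped entirely, so net volumes of zero are plausible. With 10% zeros in each arm (assumed; CV 60%, ρ 0.5, baselines above 200 ml), log-ANCOVA with a 10 ml offset has 24% power v 48% for percent change. With 15% zeros on octreotide and 5% on control, log-ANCOVA has 41%, 52% or 67% for offsets of 1, 10 or 50 ml, v about 70% for percent change. In every setting run, rank-based or untransformed baseline-adjusted models matched or beat the percent-change t-test to within about 2 points.

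**The case against.** - **Pilot status.** No power target is stated, so none is missed. This stands. The cost is a wider interval, not a broken promise.
- **Validity.** A reader might infer that comparing percent change is biased. The documents do not support that: under random assignment it is a valid comparison, only a less efficient one.
- **A fixed power loss.** A reader might infer a loss of up to about 24 points. That figure needs an assumed low correlation and wide spread, none of which is in the documents. It is also not a ceiling. Scanning reductions of 25-60%, the largest gap was 27 points with unrestricted baselines (log-SD 0.6, ρ 0.3) and 16 with all baselines above 200 ml.
- **The entry threshold limits small denominators.** This stands in part. The threshold applies at entry, but baseline is collected in the 24 hours after screening, and nothing requires that volume to exceed 200 ml. Both cases are therefore shown.
- **The t-test is not in the plan.** Correct. It is a generous stand-in, since the one named test does worse once a cut-off is imposed.
- **Log-ANCOVA is the obvious remedy.** A reader might infer that it is always better. Step 8 shows that a modest share of zeros reverses its advantage and makes the result depend on an arbitrary offset.
- **Follow-up ends at extubation or withdrawal.** Later volumes may be informatively missing. Baseline adjustment does not solve this, and the figures above assume complete data.

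**Conclusion.** The point holds and should be corrected. The plan names no test that fits its primary outcome as defined, makes the only suitable analysis conditional on grounds that do not apply, and does not name the collected baseline as a covariate.

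Over the three settings with a 40% reduction and no zero volumes, a t-test on percent change loses about 0 to 15 points of power to a baseline-adjusted log-volume analysis if all baselines exceed 200 ml, and about 0 to 23 points if they do not. Where correlation is high and spread small, there is no material loss. Only part of the gap comes from baseline adjustment; the rest comes from the scale. Fisher's test on a dichotomised change is the costlier route, at 28-34% power v 80% in the case examined.

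The direction follows from the variance formula in the linear case. The sizes rest on assumed inputs and measure lost precision, not failure against a stated power. A zero-tolerant form on the original scale should not be expected to recover the whole log-scale gain.

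**What to change.** In Statistical analysis, for the secretion outcome:

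1. Make the primary analysis a baseline-adjusted comparison of net 24-hour volume, with arm and baseline volume as terms, in all randomised patients with a post-baseline volume.
2. Delete the sample-size and cell-count condition for this outcome.
3. Name the primary 24-hour period, or use one repeated-measures model over the three periods, and say how periods after extubation or withdrawal are treated.
4. Use a form that tolerates zeros: volume on its original scale, with a rank-based ANCOVA as a check. Use the log scale only if no net volume is zero or negative, by a rule fixed before the data are seen.
5. Report the arm difference with a 95% confidence interval.
6. Keep percent change as a descriptive summary, and reserve Fisher's exact test for extubation yes/no.

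The cost is SAP wording, with no new data or patient burden. The model uses one degree of freedom (27 instead of 28), and the effect is in ml rather than percent unless re-expressed.

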As described above, scopolamine is one of the interventions routinely used by intensivists to manage excessive bronchial secretions in patients who have failed the standard measures. Similarly to octreotide, it inhibits both bronchial and gastrointestinal secretions. Remarkably, in a recent randomized control, octreotide was shown to be superior to scopolamine for symptom control in patients with increased gastrointestinal secretions due to bowel obstruction ^{13,14}.

Given the fact that no quality evidence-based information is available to guide ICU clinicians in management of bronchorrhea that has failed to respond to standard interventions, as well as the promising results described in case reports, we propose a randomized controlled trial that would compare effectiveness of octreotide to other interventions that have been used to control bronchial secretions in mechanically-ventilated patients.

Octreotide is widely available and has a relatively low cost (about \$17/day in our hospital). In the United States, it has been used widely in outpatient and inpatient settings for over 16 years, mostly for various endocrinopathies and gastrointestinal variceal bleeds but also for a number of other pathologies. It is considered by clinicians to be an overall well-tolerated medication, with fewer significant side-effects compared to systemic steroids and scopolamine. If octreotide is proven to be an effective mucoregulator, it may become an essential tool used in the intensive care units throughout the world.

Objectives/Purpose of the study:

The purpose of this study is to evaluate effectiveness of including parenteral octreotide (12-25 mcg/hour for 72 hours) in addition to the other standard of care treatments deemed necessary by the ICU attending physician in managing bronchorrhea in mechanically ventilated patients. It is hypothesized that octreotide decreases excessive bronchial secretions and shortens time to extubation.

Trial Design:

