Medications and procedures performed as part of the standard of care while the patient is on octreotide (for the "Octreotide" group) and 24 hours after admission (for the "Routine Care" group) will be recorded for the next 72 hours or until extubation or withdrawal from the study, whichever occurs earlier. Additionally, for patients in the "Octreotide" group, the rate, dose and mode of octreotide administration will be recorded on an octreotide administration log. The rate of bronchial secretions will be measured and recorded twice daily; the changes, relative to the baseline measurements, will be compared between the groups.

[figure not shown]

Figure 1. Trial design.

Electronic medical records of the subjects will be retrospectively reviewed to collect the following data recorded by the Primary Team during the ICU stay: demographic information, past medical history, smoking history, diagnoses and problem list, vital signs, diagnostic test data, medications, and procedures performed during the entire length of stay during which the subjects participated in the study.

If a patient has decision-making capacity, an informed consent will be obtained from the patient. Otherwise, an informed consent will be obtained from the person who has a legal authority to make healthcare decisions for the patient.

To minimize bias, patients will be randomized into the two groups of 15 using a random list generator (<http://www.random.org/lists/>). The research coordinator will be responsible for maintaining randomization and will place treatment assignments into security envelopes, which will be stored in the ICU intensivist workroom with code-protected entrance.

Each participant's involvement in the study is expected to last approximately 72 hours, plus the time that is necessary to ensure accurate measurement of baseline secretions rate (for up to 24 hours).

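### Extubation within 72 hours is scored with no requirement that the patient stays extubated, so the secondary outcome can misstate the effect on coming off the ventilator, in either direction

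*Combined protocol and SAP*

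**What the plan says.** The Assessment of Efficacy section names as the secondary outcome "the percentage of patients who were extubated within 72 hours after initiating the interventions". The Statistical analysis section restates it as the proportion extubated, "defined as both time to extubation AND yes/no extubated within 72 hours", and plans Fisher's exact test at the 0.05 level. The Objectives section hypothesises that octreotide reduces secretions and "shortens time to extubation".

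Under Trial Design, the study is open-label, the ICU attending opens the allocation envelope, and "Patients will be randomized into two groups of 15". The same section says "These interventions will be continued for 72 hours or until extubation" or withdrawal, and it gives the same end point for prospective recording of medications and procedures. It also says that the treating and study teams may overlap, so the attending may be an investigator. A retrospective chart review is to collect, among other items, "procedures performed during the entire length of stay during which the subjects participated in the study".

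The plan does not mention re-intubation, an observation window after extubation, the reason for extubation, or how a death is counted in this outcome.

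**The concern.** Patients enter because secretions are judged a major barrier to extubation, and the benefit hoped for includes a shorter time on mechanical ventilation. A patient who is extubated and soon re-intubated has not clearly gained that, yet scores in full on both the yes/no and the time version of the outcome.

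Three design features make this more than a drafting gap. The clinician deciding on extubation knows the allocation and may be an investigator. Study drug stops at the moment the event is scored, so any return of secretions falls outside the outcome. Prospective recording of procedures stops at the same moment.

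This is the only patient outcome beyond secretion volume, and the plan intends the results to guide local clinicians and inform larger studies. A crude rate that hides failed extubations would carry over into both uses.

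**Working it through.** The plan states no figure to reproduce: it gives no extubation rate, re-intubation rate or effect size, and says that "a power calculation to estimate the sample size cannot be performed reliably".

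**Inputs.** From the documents: 15 per arm and Fisher's exact test at 0.05 (sidedness not stated; two-sided assumed). Assumed: crude extubation of 40% on control and 60% on octreotide, with the failure rates shown below.

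**Step 1: apply the definition literally.** Patient A is extubated at 60 h and stays off the ventilator. Patient B is extubated at 60 h and re-intubated at 66 h. Both score yes within 72 h, and both have a time to extubation of 60 h. The outcome cannot tell them apart.

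**Step 2: effect on the difference.** Durable rate = crude rate × (1 − share of extubations that fail).

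| Failure, control | Failure, octreotide | Durable, control | Durable, octreotide | Difference |
|---|---|---|---|---|
| 10% | 10% | 0.40 × 0.90 = 0.36 | 0.60 × 0.90 = 0.54 | 18 points |
| 10% | 20% | 0.36 | 0.60 × 0.80 = 0.48 | 12 points |
| 10% | 30% | 0.36 | 0.60 × 0.70 = 0.42 | 6 points |
| 20% | 5% | 0.40 × 0.80 = 0.32 | 0.60 × 0.95 = 0.57 | 25 points |

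The crude difference is 20 points throughout. With equal failure shares the ratio is unchanged (0.54/0.36 = 0.60/0.40 = 1.5) and only the absolute difference shrinks. With unequal shares the crude figure can overstate or understate the durable effect.

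**Step 3: sensitivity at this sample size.** One patient is 1/15 = 6.7 points. The smallest octreotide counts reaching p < 0.05 for control counts of 2 to 5, and the p-value after recounting one or two octreotide extubations as failed, are:

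| Octreotide v control | p | One recounted | Two recounted |
|---|---|---|---|
| 9 v 2 | 0.021 | 0.0502 | 0.109 |
| 10 v 3 | 0.025 | 0.060 | 0.128 |
| 11 v 4 | 0.027 | 0.066 | 0.139 |
| 12 v 5 | 0.025 | 0.066 | 0.143 |

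These are threshold results, so losing significance after one recount is built in. The table shows how narrow the margin is, not what is typical.

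**Step 4: no true difference in durable extubation.** Suppose durable extubation is equal in both arms (20%, 30% or 40% of patients) and failed extubations are added, now as a percentage of all patients in the arm. Exact binomial enumeration gives the chance that the crude outcome significantly favours octreotide:

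| Failed, octreotide v control | Chance |
|---|---|
| 0% v 0%, or 5% v 5% | 0.8% to 0.9% |
| 15% v 5% | 3.2% to 3.5% |
| 25% v 5% | 9.5% to 10.1% |
| 30% v 0% | 22.8% to 24.6% |

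By symmetry, exchanging the arms gives the same chances of a result favouring control.

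**The case against.** The strongest objection is that the plan measures what it hypothesises. The stated hypothesis concerns time to extubation, and the outcome records exactly that. Durable liberation is arguably the better construct, but the plan does not name it as the objective. The plan also never says that a re-intubated patient is a success: it is silent, and the scoring follows from reading the definition literally. Both points are fair. Still, the definition as written is complete enough to be applied, and nothing elsewhere changes the result for a patient re-intubated early.

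A reader might infer that the definition favours octreotide. The documents do not support that. The same rule applies to both arms, and bias towards octreotide needs more failed extubations on octreotide, for which there is no evidence. If octreotide reduces secretions as hypothesised, it could have fewer failures, and the crude outcome would then understate its benefit.

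A reader might also infer that comfort-care extubation is a major part of the problem. Enrolled patients must be in weaning, so it is likely to be uncommon, although no exclusion rules it out. Re-intubation carries the point.

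Nor can it be assumed that the planned chart review already holds everything needed. It lists procedures for the whole stay, but not vital status or reason for extubation. The plan does not say whether time to extubation is truncated at 72 h, so it cannot be claimed that later times are ignored.

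Finally, this is the secondary outcome of a self-described pilot, the primary outcome's definition is unaffected, and re-intubation is itself decided open-label. The last point stands: a durability requirement reduces the problem of unblinded decisions but does not remove it.

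**Conclusion.** The point holds as a gap in the outcome definition with unknown direction. Read literally, early re-intubation and durable extubation score identically, in a setting where the decision is unblinded and both treatment and prospective recording end at the scored event. Under the assumed crude rates, a 20-point difference could correspond to a durable difference of anywhere from 6 to 25 points across the failure rates shown. With 15 per arm, a single patient moves an arm by 6.7 points and can decide a borderline test. If failure shares are equal in the two arms, the consequence is mainly a smaller absolute difference, not a false signal.

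All extubation and failure rates here are assumptions, because the documents give none. The change is worth making before analysis, with the weight proper to a secondary outcome in a pilot.

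**What to change.** - Define the outcome as extubated within 72 h of starting the interventions and alive without re-intubation through a prespecified window. The investigators should choose and justify its length; 48 h is an example, not a figure from the documents.
- Count death before extubation, and any extubation for withdrawal of support, as non-success.
- Apply the same definition to time to extubation, that is, time to the first extubation that meets it, and state how deaths are handled. Treating death as a competing event is one option, but it will be imprecise with 15 per arm.
- Report crude 72-hour extubation as supportive, so that the result stays comparable with the present definition.
- Take re-intubation from the whole-stay procedure review already planned under Trial Design, and add vital status and reason for extubation as explicit chart fields.

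The cost is a revision to the outcome wording, two added chart fields and extraction of re-intubation from records already under review. The event rate will be slightly lower and the outcome known somewhat later: with a 48 h window, at most 72 + 48 = 120 h after the interventions start. No extra patients or visits are needed.
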